#### 4.4 Participant Management

#### 4.4.1 Clinical management

A limited predefined management protocol will enhance the success of this pragmatic trial:

- A summary of the research management algorithm for patients in each of the two study groups will be strategically posted at clinic locations and will be placed in each participant's medical record; trained clinical (or research) staff will be available to measure pragmatic clinic BP at each visit.
- Routine pregnancy care at each center will be given to patients by clinical providers trained in the study protocol.

- Prescribed antihypertensive therapy according to study protocol will be supplied by the research team or designated pharmacist at each center/site until at least the time of delivery. After delivery the study medication or another appropriate antihypertensive agent will be used for at least 2 weeks after delivery.
- Prenatal visits will generally occur per local clinical standards at each site: every 1-3 weeks until 32-34
  weeks gestation when weekly or more frequent visits will be indicated (depending on antenatal testing
  initiation policy) at the discretion of the provider.
- After 20 weeks, standard clinical care suggests that preeclampsia should be excluded by a clinical diagnostic work-up (including urine protein, serum creatinine, CBC and liver enzymes as necessary) and adherence to therapy considered before enrolling patients or escalating dose due to elevated BP.
- Patients will receive lifestyle modification counseling per the routine clinical practice at each center for any
  patient with hypertension (nutrition counseling, exercise/physical activity advice and smoking and/or alcohol
  cessation interventions).
- Ultrasound for anatomy or fluid/growth and antenatal testing will be per clinical center's routine.
- Timing of delivery preferably no earlier than 38-39 completed weeks unless indicated earlier for obstetric or medical reasons according to local guidelines (consistent with ACOG recommendations)

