#### Adherence to antihypertensive medications will be assessed as follows:

- a) The clinical provider (with the help of study staff as applicable) will assess adherence according to usual clinical routine to determine whether the participant has been adherent within the past 24 hours. For example, the provider could ask "When was the last time you took your medication? "Do you take your medication every day?" The provider will use this information to determine whether to titrate the BP medication dose(s) as clinically indicated.
- b) At clinic visits when the patient requires a medication refill, study staff will conduct a pill count of the patient's study medication and record it. This will be used to estimate adherence. Given the pragmatic nature of the study, a more elaborate plan to monitor adherence will not be implemented by the research team.

All participants will be probed about off-study use of antihypertensive medication(s), alternative medications, and other vasoactive drugs during the clinic visit. Appropriate sources of this information include participant (or significant other) report, current pharmacy action profiles, and verification of medications documented in the medical record.

In the standard comparison group, labetalol treatment will be started only for BP ≥160/105. Only the lowest dose needed to give keep BP below this level will be given. Methyldopa or other clinically acceptable medication at the discretion of the clinical provider will be the third-line medication (after maximum tolerated doses of both labetalol and nifedipine ER) in the unlikely situation that a third medication is needed.

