#### 5.1.1 Original Sample Size

We used data from the MFMU Network's High Risk Aspirin study (enrollment into the CHTN group was based on pragmatic clinic BPs) to estimate the frequency of the composite outcome components among 763 women with mild CHTN at baseline as follows: Fetal or neonatal death = 6.16%; severe preeclampsia (severe hypertension and proteinuria, eclampsia, preeclampsia with thrombocytopenia, creatinine>1.4, elevated liver enzymes) =0.66%; abruption =1.46%; indicated PTB <35 weeks =12.32%. The frequency of the primary composite outcome was 16%. Assuming a 2-sided alpha of 0.05 and conservative baseline incidence of 16% (since this is regardless of BP lowering therapy, and we expect the incidence to be higher in those not receiving therapy) the unadjusted sample sizes/arm needed to detect a 20-30% reduction in the primary outcome with 85-90% power are presented in Table 5. These unadjusted estimates do not take into account drop-ins and drop-outs or the interim look we propose. We assume: the 10% of the control group that will require treatment for severe hypertension are already well-accounted for in our baseline rate of 16% estimated from usual care; that in addition there will be up to a 10% rate of protocol violations (treatment in the control group without meeting criteria for severe hypertension) and that nonadherence in the treatment arm is 10%. The adjusted outcome rates for 25% reduction are: 15.6% and 12.4%, and the revised adjusted sample sizes/arm accounting additionally for 8% loss-to-follow up are presented in Table 5.

Table 5: Estimated sample size/arm (30%, 25% and 20% Reductions) under original plan

	30% REDUCTION		25% REDUCTION		20% REDUCTION	
Power	Unadjusted	Adjusted	Unadjusted	Adjusted	Unadjusted	Adjusted
90%	1075	1829	1587	2696	2539	4314
85%	919	1561	1356	2305	2170	3687

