## 5.3.1 Primary Aims

Standard comparisons of characteristics between groups will be conducted at baseline. It is anticipated that the randomization scheme will balance the groups for these covariates (considering the large sample size) and they will not be adjusted for in the primary analyses. However, secondary analyses of relevant outcomes using regression adjustments will be implemented to account for any suggested confounding covariates that are unbalanced between study groups. The potential adjustment covariates include baseline BP level, race/ethnicity, smoking status, prior anti-hypertensive use (known CHTN), gestational age at baseline and weight. Per protocol analyses, which reflect adherence to antihypertensive therapy will be conducted in secondary analyses.

The primary analysis will compare the incidence of the composite outcome and SGA between the 2 study groups – a chi-square p-value and the RR and 95% CI (relative to ACOG comparison group) will be computed and followed up with a logistic regression comparison which will take into account the duration of therapy, GA at initiation of therapy and other covariates. Event free survival will be calculated using Kaplan Meier estimates and tested using a log rank test. Student's t-test comparisons of continuous outcomes (duration of hospital, NICU stay, etc.) will be conducted.

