### 4. Additional Analyses

For the primary outcome, both intent-to-treat (as the primary) and a per-protocol approach will be used. The per-protocol population will be defined as those individual in the Lower BP (treatment) group who have >80% compliance and attendance at all scheduled visits. No adjustments will be made in the Standard Group since this provides our pragmatic control group. Secondary analyses will be examined accounting for the duration of therapy, prior antihypertensive therapy, race/ethnicity, pre-existing diabetes, GA at initiation of therapy and other covariates.

Pre-pregnancy and/or early pregnancy BMI will be evaluated for possible effects on all outcomes. Sensitivity analyses will be conducted to examine these possible effects. We will also evaluate potential interactions between BMI and treatment assignment. Subgroup analyses (by BMI class) will be explored where warranted. Similar interactions with other key patient characteristics will be examined.

Event free survival for the first occurrence of any of the primary outcome composite variables and will be calculated using Kaplan Meier estimates with testing via a log rank test. Student's t-test for comparisons of continuous outcomes (duration of hospital, NICU stay, etc.) will be conducted as well as regression analyses adjusting for pertinent covariates.

4.1 Secondary Aims/Hypotheses: Secondary outcomes will be compared using methods and approaches outlined above. The incidence of each of the 3 outcomes for this aim (perinatal death, composite neonatal morbidity, and composite of severe maternal morbidity) will be compared by completed weeks. To investigate the impact on the timing of delivery, longitudinal analysis of the full trial cohort with treatment arm as a key covariate, using completed gestational age (weeks 36-40) and their interaction as the independent variable will be implemented to assess the incidence of each of the 3 outcomes. The OR (95% CI) at each gestational age relative to 39 weeks will be computed and then adjusted for relevant covariate characteristics using logistic regression. Additional analyses will involve computing the adjusted OR and 95% CI for each outcome given delivery at a specific gestational age vs. at term. We will assess whether there is a gestational age beyond which waiting to deliver might be harmful.

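### The per-protocol set filters only the Lower BP arm, on a visit count that the primary outcome itself can shorten, so this secondary contrast is biased in a direction the documents do not fix.

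*Combined protocol and SAP*

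**What the plan says.** SAP section 4 (Additional Analyses) states that for the primary outcome "both intent-to-treat (as the primary) and a per-protocol approach will be used". It restricts the per-protocol set to "those individual in the Lower BP (treatment) group who have >80% compliance and attendance at all scheduled visits" and adds: "No adjustments will be made in the Standard Group since this provides our pragmatic control group".

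Protocol section 5.3.1 is less specific: "Per protocol analyses, which reflect adherence to antihypertensive therapy will be conducted in secondary analyses". It has no attendance test and no one-arm rule. Both come from the SAP alone.

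Visits follow protocol section 4.4.1: "Prenatal visits will generally occur per local clinical standards at each site: every 1-3 weeks until 32-34", then "weeks gestation when weekly or more frequent visits will be indicated", at the provider's discretion. Section 4.5 adds a postpartum visit at 6 (4-12) weeks. Neither document says which of these count as scheduled, or whether the count stops at delivery.

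On compliance, protocol section 4.4.2 says that when a refill is needed "study staff will conduct a pill count of the patient's study medication and record it". The same section has providers and staff ask about adherence, and names participant report, pharmacy profiles and medical records as sources on off-study medication.

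For the control arm, protocol section 5.1.1 plans that "there will be up to a 10% rate of protocol violations (treatment in the control group without meeting criteria for severe hypertension").

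**The concern.** A per-protocol set should not select women by a quantity that the endpoint determines. Indicated birth before 35 weeks ends the pregnancy at about the point where visits become weekly. A woman delivered at 32 weeks has fewer appointments to miss than one delivered at 38 weeks. An all-visits rule therefore treats women with and without the outcome differently even if they attend equally reliably. Because the rule acts only on the Lower BP arm, nothing on the other side offsets it.

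The unfiltered Standard arm also keeps women treated without meeting criteria, a deviation that a per-protocol contrast would usually address.

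At stake is the one named adherence analysis of the primary outcome. The trial is open-label and the plan allows for 10% noncompliance and 10% crossover, so readers will look to this analysis for the effect among women who took treatment.

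**Working it through.** **Plan figures.** The documents give no figure for the per-protocol set. To confirm that the planning rates are read correctly: 16% with a 33% reduction is 0.16 × 0.67 = 0.1072. A two-proportion formula (pooled variance, two-sided 0.05, 85% power) gives 745 per arm against the stated 748. With 10% crossing each way the rates are 0.9 × 0.16 + 0.1 × 0.1072 = 0.1547 and 0.9 × 0.1072 + 0.1 × 0.16 = 0.1125. These give 1164 against the stated 1142. Then 1142/0.95 = 1202.

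**Inputs from the documents.** Standard rate 16%; Lower BP rate 16% (no effect) or 10.72%; share of events that are early indicated births 12.32/16 = 0.77 (protocol section 5.1.1).

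**Assumptions (not in the documents).** Randomization at 16 weeks; visits every 2 weeks, weekly from 33 weeks; early events deliver at 32 weeks and all other women at 38. That is 7 and 12 prenatal visits, or 8 and 13 with one postpartum visit. Each visit is attended independently with probability a. The >80% compliance criterion is set aside at first.

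**Reading A: the count stops at delivery (plus the postpartum visit).**
- Event women pass with probability s_E = 0.77a^8 + 0.23a^13.
- Other women pass with probability s_N = a^13.
- Per-protocol rate = p·s_E / [p·s_E + (1−p)·s_N]; RR = rate / 0.16.

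Example, no effect, a = 0.95: s_E = 0.77 × 0.6634 + 0.23 × 0.5133 = 0.6289. Rate = 0.16 × 0.6289 / (0.16 × 0.6289 + 0.84 × 0.5133) = 0.1892. RR = 1.18.

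| a | Lower BP arm kept (no effect) | RR if true RR 1.00 | RR if true RR 0.67 |
|---|---|---|---|
| 0.99 | 88% | 1.03 | 0.69 |
| 0.97 | 69% | 1.10 | 0.75 |
| 0.95 | 53% | 1.18 | 0.80 |
| 0.90 | 28% | 1.41 | 0.97 |

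If only 30% of events are early deliveries, the no-effect RR is 1.01 to 1.17 over the same range of a.

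**Clustered attendance, same 95% mean, no effect.**
- 80% of women attend everything and 20% attend each visit with probability 0.75. The pass probabilities are 0.8 + 0.2 × 0.75^8 = 0.8200 and 0.8 + 0.2 × 0.75^13 = 0.8048, so s_E = 0.8165 and RR = 1.01.
- Half attend at 0.99 and half at 0.91. The pass probabilities are 0.6965 and 0.5855, so s_E = 0.6710 and RR = 1.12.

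**Reading B: a full-term schedule is required.** Early deliverers cannot qualify. Rate = p(1−share) / [p(1−share) + 1 − p]. With no effect:
- share 0.77: 0.0368/0.8768 = 4.2%, RR 0.26
- share 0.50: 0.08/0.92 = 8.7%, RR 0.54
- share 0.30: 0.112/0.952 = 11.8%, RR 0.74

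**Offsets under Reading A at a = 0.95.** The bias cancels if women without the event are 0.6289/0.5133 = 1.23 times as likely to pass >80% compliance. It also cancels if event women have about 4 extra scheduled visits (RR 1.00; with 6 extra, 0.92).

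**Same rule in both arms, equal attendance.** The no-effect RR is 1.00, and a true 0.67 appears as 0.67 to 0.69 for a from 0.97 to 0.90. Most of the distortion therefore comes from filtering one arm.

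**The case against.** A reader might infer that the rule must bias against treatment and could hide a real benefit. The documents do not support that. Scheduled visits are undefined, a full-term count reverses the sign, and the compliance criterion or extra visits for worsening disease can cancel the effect. Severe preeclampsia near term or postpartum shortens the schedule little or not at all.

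The 77% share may not carry over either. It comes from planning data with severe preeclampsia at 0.66% under a narrower definition, and protocol section 5.1.2 reports an overall event rate above expectation. Independent attendance is also only an assumption, and strong clustering nearly removes the effect. These objections stand against any single direction or size.

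A second tempting inference is that women on drug not supplied by the study cannot show >80% compliance. The SAP does not say that compliance means pill count, and protocol section 4.4.2 describes other sources. What stands is that the SAP gives no compliance rule for these women.

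Leaving the Standard arm whole is a stated choice, made because it is the pragmatic control. Filtering it by treatment received would also select after randomization and might remove women with rising blood pressure. That is a fair defence of not filtering the control arm. It does not justify an outcome-dependent attendance test in the other arm.

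Finally, intention-to-treat is primary, with imputation, complete-case and best/worst-case analyses. A benefit found there is not hidden by this set.

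**Conclusion.** The concern holds as a defect of a secondary analysis. As written, the set is one-sided, conditions on behaviour after randomization, and depends on pregnancy length, which the primary outcome helps determine. No other section repairs it.

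Direction and size are not established. With no true effect, the illustrative RR is about 1.01 to 1.4 if visits count to delivery, and about 0.26 to 0.54 if a full-term schedule is required (with 77% and 50% of events early). These figures rest on assumed visit counts, attendance of 90% to 99%, its clustering, and the early-event share. They also set aside the compliance criterion. An undefined term that can move the result to either side of 1 should be settled before the data are analysed. No decision rule in the documents uses this set.

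**What to change.** In SAP section 4:

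1. Delete the criterion of attending all scheduled visits.
2. Define Lower BP compliance as the proportion of prescribed doses taken from randomization to the first primary event or delivery. Use pill count for study-supplied drug, and participant report, pharmacy or medical record otherwise. Keep the >80% cut.
3. Adjust the per-protocol estimate for baseline risk factors already collected (protocol sections 5.2 and 5.3.1).
4. Report it as an asymmetric supportive analysis, not as a like-for-like comparison of adherers.
5. Optionally, add a sensitivity analysis that also excludes Standard-arm women who deviated from the protocol's own treatment criteria, noting that this too selects after randomization.

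The cost is SAP wording and a little programming; the protocol already provides for dispensing, visit and off-study medication data. The downside is less exact compliance data for women on drug not supplied by the study.

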#### 3.2b Secondary Research Aims Unrelated to Primary Question:

- d) To assess whether antihypertensive treatment of mild CHTN during pregnancy (compared to withholding therapy) influences post-pregnancy adherence to recommended therapy.
- e) To assess the impact of postpartum treatment recommendations on maternal outcomes
- f) To investigate the optimal gestational age to deliver women with CHTN in order to minimize maternal and perinatal complications. We will apply survival analysis methods to the trial population.
- g) To collect and store biospecimens including maternal and cord blood for future biological and biophysical studies to understand the effects of antihypertensive therapy in pregnant women with mild CHTN.
- h) To compare outcomes by standardized pragmatic clinic BP vs. standardized automated clinic BP measures.

- i) To assess whether the effect of therapy on SGA differs by whether current national standard nomogram vs. individualized nomogram for birth weight is utilized.
- j) To plan for a long-term follow-up study to evaluate the impact of treatment of mild-moderate chronic hypertension on long-term maternal and child outcomes

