### 5.3.2 Secondary Aims

The secondary outcomes will be similarly compared. The incidence of each of the 3 outcomes for this aim (see 3.1.5 b ii) will be compared by completed weeks. To investigate the impact on the timing of delivery), longitudinal analysis of the full trial cohort with treatment arm as a key covariate, and completed gestational age (weeks 36-40) and their interaction as the independent variable will be implemented to assess the incidence of each of the 3 outcomes. The OR (95% CI) at each gestational age relative to 39 weeks will be computed and then adjusted for relevant covariate characteristics using logistic regression. Additional analyses will involve computing the adjusted OR and 95% CI for each outcome given delivery at a specific gestational age vs. at term. We will assess whether there is a gestational age beyond which waiting to deliver might be harmful.

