- **4.4. Other monitored outcomes:** The list below identifies individual outcomes that will be examined as secondary and tertiary outcomes following the study's primary analysis. Additional secondary analysis concepts may be submitted to the Publications Committee for review, feasibility assessment, and ranking/queueing. Procedures for submissions are available in the CHAP Publications Guidelines document.
- 8) Timing of delivery outcomes: The risks of 3 key outcomes, a) perinatal death, b) composite neonatal morbidity and c) composite of severe maternal morbidity (defined above) will be examined in relation to gestational age (completed weeks from 36 to 40 weeks) using longitudinal analysis methods to determine the delivery gestational age at which risks nadir (see analysis section).
- 9) Adherence to treatment at 6 (4-12) weeks postpartum: The follow-up questionnaire will include items to assess adherence to antihypertensive therapy since delivery.

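### The delivery-timing analysis judges waiting from odds ratios by week of delivery, with no comparison group of ongoing pregnancies and no account of why women were delivered early

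*Combined protocol and SAP*

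**What the plan says.** The timing aim is described in several places.

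- **Aims (protocol 1.3b c and 3.2b f).** The optimal gestational age for delivery will be investigated, and "We will apply survival analysis methods to the trial population".
- **Outcome lists (protocol 4.7.2 item 5, SAP 4.4 item 8).** Perinatal death, composite neonatal morbidity and composite severe maternal morbidity are examined over completed weeks 36 to 40 by longitudinal methods, "to determine the delivery gestational age at which risks nadir". Protocol 4.7.2 refers to the analysis section for the method.
- **Analysis sections (protocol 5.3.2, SAP 4.1).** A longitudinal analysis of the whole cohort takes completed gestational age, with its interaction with arm, as the independent variable. Then: "The OR (95% CI) at each gestational age relative to 39 weeks will be computed", followed by a logistic regression that adjusts for covariates described only as relevant. Further analyses involve "computing the adjusted OR and 95% CI for each outcome given delivery at a specific gestational age vs. at term".
- **The conclusion to be drawn.** "We will assess whether there is a gestational age beyond which waiting to deliver might be harmful".

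Protocol 4.4.1 states how delivery is timed in the trial: "Timing of delivery preferably no earlier than 38-39 completed weeks unless indicated earlier for obstetric or medical reasons according to local guidelines".

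**The concern.** At week w the choice is between delivering now and continuing. Women who continue may deliver in any later week, and they carry every risk met on the way. Delivery at 39 weeks is only one of those later results, reached by women who had no earlier reason to be delivered.

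The planned contrast departs from that choice in two ways. First, under protocol 4.4.1 women delivered at 36 or 37 weeks are largely those with an indication, so their outcomes reflect the complication as well as the week. Second, a complication that arises at 38 weeks in a woman who was well at 36 counts against delivery at 38 weeks, not against the decision to wait at 36.

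Protocol 2.7.2 calls delivery timing controversial and says that relating outcomes to gestational age at delivery will help define the optimal window. A conclusion from this contrast could reach practice while reflecting selection.

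**Working it through.** **No figure to reproduce.** The documents give no sample size, power or weekly rates for this aim. The check is therefore a reading of the text plus two illustrations with assumed inputs.

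**Step 1: does any wording supply the missing comparison?**

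- *Survival methods.* They are named in the aims, but neither analysis section specifies one for this aim. The Kaplan-Meier text in SAP section 4 concerns first occurrence of a component of the primary composite.
- *Longitudinal model.* Its independent variable is completed week 36 to 40. No risk set of women still pregnant is defined.
- *Covariates.* None are listed for this aim. For the primary-aim regressions, protocol 5.3.1 says "The potential adjustment covariates include baseline BP level, race/ethnicity, smoking status, prior anti-hypertensive use (known CHTN), gestational age at baseline and weight", all known at baseline. SAP section 4 adds items such as duration of therapy and pre-existing diabetes. Neither names the indication for delivery or the woman's status at week w.
- *Term.* It is not defined. If it is the complement of preterm birth before 37 weeks (protocol 4.7.2), it contains most of the weeks compared with it.

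Order in time adds to the problem. The maternal composite includes pulmonary edema and renal failure, and pulmonary edema and raised creatinine are also among the criteria for preeclampsia with severe features in protocol 4.7.1. Such an event can prompt the delivery and then be counted as an outcome of that week. An antepartum fetal death likewise precedes its delivery week.

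**Step 2: week of delivery changes nobody's risk.** Assumptions: risk 1% without an indication and k times that with one, k = 3 to 5; share s of deliveries that are indicated = 0.40-0.60 at 36 weeks, 0.30-0.40 at 37, 0.15 at 39.

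Risk in a week = s × k × 0.01 + (1 − s) × 0.01. The OR is the ratio of odds against 39 weeks.

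- Lowest at 36: k = 3, s = 0.40: 0.018 against 0.013, OR 1.39.
- Highest at 36: k = 5, s = 0.60: 0.034 against 0.016, OR 2.16.
- At 37: 0.016 against 0.013 gives OR 1.23; 0.026 against 0.016 gives OR 1.64.

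An OR well above 1 appears although the week has no effect.

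**Step 3: waiting is harmful by construction.** Assumptions: each week a complication arises with probability h, prompts delivery and carries outcome risk p. Otherwise delivery occurs with probability e = 0.05, 0.12, 0.30, 0.70, 1.0 at weeks 36 to 40, with risk 1% in every week. Delivering an uncomplicated woman early is then never harmful, and waiting always adds risk.

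Indicated share in a week = h / (h + (1 − h)e). For h = 0.05 and p = 0.10:

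- Week 36: 0.05 / 0.0975 = 0.513; risk = 0.513 × 0.10 + 0.487 × 0.01 = 0.0562.
- Week 39: 0.05 / 0.715 = 0.070; risk = 0.0163.
- OR = (0.0562 / 0.9438) / (0.0163 / 0.9837) = 3.59.

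The same calculation over three scenarios:

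| Contrast | h 0.03, p 0.05 | h 0.05, p 0.10 | h 0.10, p 0.20 |
|---|---|---|---|
| Planned OR, 36 vs 39 | 2.19 | 3.59 | 4.39 |
| Planned OR, 40 vs 39 | 0.96 | 0.89 | 0.80 |
| OR, all delivered at 36 vs all still pregnant after 36 | 1.95 | 2.71 | 2.76 |
| Risk ratio, continuing beyond 36 vs uncomplicated delivery at 36 | 1.31 | 2.15 | 5.61 |
| Risk ratio, continuing beyond 39 vs uncomplicated delivery at 39 | 1.12 | 1.45 | 2.90 |

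The planned ORs would be read as early delivery being worse and waiting being safe, the opposite of what was built in. Changing only the comparator to all ongoing pregnancies (third row) reduces the bias but leaves the sign wrong, because indicated deliveries remain in the delivered group. Restricting to women without an indication gives the right direction.

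**The case against.** The plan is under-specified rather than plainly wrong. It names survival, longitudinal and logistic methods, and it promises adjusted odds ratios as well as crude ones. An analyst could choose covariates for indication or build a proper risk set, so it goes too far to say that the analysis could never answer the question. That stands as a limit. Still, protocol 4.7.2 points to the analysis section for the method, and the text there conditions on week of delivery.

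A reader might infer that the method will favour 39 weeks whatever the true effect of waiting. The documents do not support that. The tendency is for earlier weeks to look worse; in the illustration 40 weeks comes out below 39 (OR 0.80 to 0.96), and a strong real effect could outweigh the bias.

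Every numerical input above is assumed, and the ORs are crude. They show that the bias can be material; they do not estimate it for this trial.

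Finally, the aim is listed as unrelated to the primary hypothesis, is to be reported in secondary studies and is not randomised. That limits the weight of the point but does not make the contrast suitable for the conclusion drawn from it.

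**Conclusion.** The concern holds in a bounded form. As written, protocol 5.3.2 and SAP 4.1 base a conclusion about waiting on odds ratios by week of delivery, in a trial whose protocol reserves earlier delivery for indications. No ongoing-pregnancy risk set and no adjustment for indication is specified, so earlier weeks will tend to look worse and later weeks safer for reasons of selection. With no effect of week at all, the crude OR for 36 versus 39 weeks is about 1.4 to 2.2 under the stated assumptions. With waiting harmful by construction, the planned contrast points the wrong way in all three scenarios examined. The text should be changed before the timing analysis is run. It would be wrong to infer any weakness in the trial's main result: the randomised comparisons of the composite and of SGA, and the interim analysis, do not depend on this aim.

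**What to change.** In protocol 5.3.2 and SAP 4.1, replace the OR against 39 weeks or term as the basis for the timing conclusion.

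1. For each week w from 36 to 39, take women who are undelivered and have no indication for delivery at the start of week w.
2. Compare those delivered in week w without a new indication with those who continue. Count all later outcomes of those who continue, including complications that later prompt delivery.
3. Adjust for status known at the start of week w, and list those covariates.
4. State how women whose indication arises during week w are counted, since under this definition they fall on neither side that week.
5. Report perinatal death per ongoing pregnancy.
6. Reconcile the survival, longitudinal and logistic wording across the aims, outcome lists and analysis sections. Odds ratios by week of delivery can stay as description.

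The cost is analysis text and programming, provided that the visit, admission and delivery forms hold the reason for delivery and its timing, which should be confirmed. The downsides are fewer women in each weekly comparison, reliance on the recorded reason for delivery, and some remaining confounding, so the result should be labelled observational.
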